5.2.3. Analyses for Biomarkers

The skin biopsy samples will be analyzed using immunohistochemistry (IHC), gene arrays and gene expression of specific genes to elucidate the mechanism of action of Crisaborole, which will be done using Taqman Low Density Array (TLDA) PCR for 48 genes including housekeeping genes as well as single gene PCR for few genes that are below detection level on TLDA. TLDA PCR expression values are estimated by $-\Delta Ct$ that is computed relative to RPLPO housekeeping gene. Measurements under the limit of detections are imputed as 20% of the minimum value observed for that gene.

The gene expression data is modeled using a mixed effect model with Time, Tissue, and Treatment as a fixed effect and a random intercept for each patient. This formulation intrinsically models the patient correlation structure as in the case of a paired t-test, having the advantage that estimation of the main effects is possible even in the presence of missing values. This allows to use all available data at each time point rather than using only complete observations. This approach introduces less bias than restricting the analysis for those patients who completed the study. Contrasts are used to estimate the fold changes with treatment within each treatment group and conduct hypothesis testing. Changes with treatment will be estimated and per gene improvement will be defined as $-100 * (XW_{12,LS} - XW_{0,LS}) / (XW_{0,LS} - XW_{0,NL})$, $XW_{12,LS} - XW_{0,LS}$ represents the least square means for the treatment change and $XW_{0,LS} - XW_{0,NL}$ represents the least square means for the baseline differences.

The microarray data is processed using standard QC metrics and R packages. Expression measures are obtained using GCRMA algorithm. Adjustments by batch effect and clinical variables are carried out using ComBat. Probe-sets with at least 15 samples with expression

values larger than 3 are kept for further analysis. Expression values are modeled using mixed-effect models with fixed factors Time, Tissue and Treatment and a random effect for each patient. Fold changes for the comparisons of interest are estimated and hypothesis testing was conducted on such comparisons using contrasts under the general framework for linear models. P-values from the moderated (paired) t-test were adjusted for multiple hypotheses using the Benjamini–Hochberg procedure which controls the False Discovery Rate (FDR).

Additionally, extensive bioinformatics tools will be employed to gain insights into the mechanism of action of crisaborole.

Correlation analysis will be performed to assess if change from baseline in biomarkers correlates with change in the lesion TSS. Pearson correlation coefficient will be provided.

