### **9.1. Sample Size Determination**

The sample size of this study is based on the objective to demonstrate crisaborole ointment 2% is more efficacious than vehicle in the target lesion in subjects with mild to moderate AD as measured by the change from baseline in target lesion severity score (TSS) between crisaborole treated lesion and vehicle treated lesion.

Approximately 40 subjects will be enrolled in the study to ensure approximately 30 subjects who will have skin biopsy done at Day 15 during the double-blind treatment period to have the precision described below (considering the non-compliance during the double-blind treatment period is ~20%).

A sample size of 40 will have 90% power to establish the superiority of crisaborole to vehicle as measured by the change from baseline in TSS between crisaborole treated lesion and vehicle treated lesion at Day 15 using paired t-test at 0.05 (one-sided) significance level, assuming the difference is 1.4 and standard deviation 3. With sample size of 30, the power becomes 80%.

A sample size of 30 also provides the following precision to estimate the change in the key skin biomarkers S100A12, CCL17, CCL18, CCL22, elafin/PI3, K16, or IL-13 in the target lesion treated with crisaborole 2% ointment or vehicle. The expression level of biomarkers at Baseline or Day 15 will be expressed as log2 transformed fold change (FCH) relative to house-keeping gene human acidic ribosomal protein gene (hARP), ie, the ratio between expression level of each biomarker and the expression level of hARP for each RT PCR sample. The margin of error for the estimates, ie, the half width of the 95% confidence intervals (CIs) for the change from baseline in FCH, is less than 1.1 under the assumption that the maximal standard deviations for the change in FCH is 3 based on unpublished data.

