2.1.2. Secondary Objectives

- To evaluate change in other skin biomarkers of atopic dermatitis in target lesions treated with crisaborole ointment 2% or vehicle.*
- To evaluate normalization of biomarker and gene expression levels in lesional skin treated with crisaborole ointment 2% or vehicle.*
- To evaluate changes in AD clinical sign and symptom severity in target lesions treated with crisaborole ointment 2% or vehicle.*
- To assess the safety and local tolerability of crisaborole ointment 2% in subjects with mild to moderate AD.*

CCI

- CCI [REDACTED]

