6.1.2.1. Primary Analysis

- Analysis time points: Day 15.
- Analysis population: PPAS.
- Analysis methodology: the change from baseline in lesion biomarkers will be analyzed using the model specified in [Section 5.2.3](#).
- Imputation for missing values: observed data will be included in the model, the missing values will be handled in the model, where the values are assumed to be missing at random.
- Supporting objective and Decision rule: Primary Objective, the lesion biomarker change is superior for crisaborole treated area if adjusted pvalue<0.05.

Reporting results:

- Raw data: The sample size, mean, standard deviation, median, Q1, Q3, minimum and maximum at baseline and post-baseline visits will be presented for each treatment.
- Change from baseline: The sample size, mean, standard deviation, median, Q1, Q3, minimum and maximum will be presented for each treatment. The LS means of difference and the corresponding standard error, 95% CI, p-value will be presented.

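### SAP 5.2.3 sets non-detects to 20% of the gene's minimum without naming a scale; on the −ΔCt scale just defined, a negative minimum puts undetected samples above the lowest detected one

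*SAP*

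**What the plan says.** SAP Section 5.2.3 reads "TLDA PCR expression values are estimated by" −ΔCt relative to a housekeeping gene. The next sentence is the limit-of-detection rule: "Measurements under the limit of detections are imputed as 20% of the minimum value observed for that gene". It does not say whether the 20% applies to −ΔCt or to the back-transformed ratio 2^−ΔCt.

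The same section expects some non-detection, since it provides for "single gene PCR for few genes that are below detection level on TLDA". It then uses the imputed values in two ways. "Contrasts are used to estimate the fold changes with treatment within each treatment group and conduct hypothesis testing" is the first. The second is a percentage measure: "per gene improvement will be defined as" the change in lesional skin relative to the baseline lesional versus non-lesional difference.

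SAP Section 6.1.2.1, the primary analysis of the seven key biomarkers, states that "the change from baseline in lesion biomarkers will be analyzed using the model specified in" Section 5.2.3, with superiority declared on an adjusted p-value below 0.05.

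Protocol Section 9.1 describes the untransformed quantity as "the ratio between expression level of each biomarker and the expression level of hARP for each RT PCR sample", and Section 9.3 has RT PCR values log2-transformed before analysis. Neither section has a limit-of-detection rule. The statements that nothing is imputed (Protocol 9.3, SAP 4.2) concern missing data, not values below detection.

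**The concern.** A rule of the form 'a fraction of the minimum' places non-detects below everything detected only if the quantity is positive. −ΔCt is negative whenever a sample expresses less of the gene than of the housekeeping gene. Multiplying a negative minimum by 0.2 moves it towards zero, so the sample with the least expression gets a higher score than a sample in which the gene was found.

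A treatment that lowers expression also produces non-detects, so the error works against the effect being measured. At stake is the crisaborole–vehicle contrast for any key biomarker with non-detects, a negative minimum, and a change in non-detect rate that differs between the two lesions. If the rates move equally, the contrast is about unbiased. Even then, within-treatment fold changes and per-gene improvement are distorted when non-detect rates differ between visits or between lesional and non-lesional skin. That bears on the secondary objective "To evaluate normalization of biomarker and gene expression levels in lesional skin treated with crisaborole ointment 2% or vehicle".

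**Working it through.** **Inputs.** From the protocol (9.1): n = 30, SD of change 3, and a stated margin of error below 1.1. From SAP 5.2.3: the −ΔCt scale and the 20% rule. Gene abundance, non-detect rates, treatment effects and the split of variance are not in the documents and are assumed below.

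No figure in the plan rests on the imputation rule. The margin of error serves as a yardstick, and it reproduces: 1.96 × 3/√30 = 1.07 (1.12 with the t quantile).

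**1. The two readings, for a gene with minimum m.**

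- Literal, on −ΔCt: 0.2m. Distance from the minimum: 0.2m − m = −0.8m, which is positive when m < 0.
- Linear, on 2^−ΔCt and then log2: log2(0.2 × 2^m) = m − log2(5) = m − 2.32, which is below m for every m.
- Gap for m < 0: 0.2m − (m − 2.32) = 0.8|m| + 2.32.

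| m | Literal | Literal minus m | Linear | Gap |
|---|---|---|---|---|
| −4 | −0.8 | +3.2 | −6.32 | 5.52 |
| −8 | −1.6 | +6.4 | −10.32 | 8.72 |
| −12 | −2.4 | +9.6 | −14.32 | 11.92 |
| +2 | 0.4 | −1.6 | −0.32 | 0.72 |

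With a positive minimum the literal rule still orders samples correctly.

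**2. Effect on the treatment contrast (exact, complete biopsies).** Let p be the non-detect proportion by lesion (C crisaborole, V vehicle) and day. The readings differ in the contrast by

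(0.8|m| + 2.32) × [(pC15 − pC1) − (pV15 − pV1)].

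This is zero when the bracket is zero. One net extra crisaborole non-detect among 30 gives 5.52/30 = 0.184, 8.72/30 = 0.291 and 11.92/30 = 0.397 log2 units for m = −4, −8 and −12.

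**3. Effect on one lesion's change from baseline.** Net extra Day 15 non-detects needed for the readings to differ by about the protocol's margin: 6 × 0.184 = 1.10, 4 × 0.291 = 1.16, 3 × 0.397 = 1.19. These are gaps between the two readings. They are not bias from the truth, because they include the linear rule's own 2.32 offset.

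**4. Illustrative simulation.** 1500 trials per cell, n = 30, five samples per subject (non-lesional Day 1; each lesion on Days 1 and 15). Patient SD 1, lesion SD 1, residual SD 2.12 (SD of change √2 × 2.12 = 3). Non-lesional mean 3 log2 units below lesional. Random-intercept cell-means model, two-sided 0.05 test, no Benjamini-Hochberg step.

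*Unequal effects:* changes −2.0 (crisaborole) and −0.5 (vehicle), so the true contrast is −1.5. Estimated contrast under the literal rule, by baseline lesional mean:

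| Day 15 non-detects, crisaborole (vehicle) | −2 | −4 | −8 | −12 |
|---|---|---|---|---|
| 1% (0.2%) | −1.41 | −1.39 | −1.40 | −1.34 |
| 5% (1.3%) | −1.22 | −1.16 | −1.02 | −0.91 |
| 12% (3.9%) | −0.92 | −0.79 | −0.54 | −0.32 |
| 28% (12%) | −0.50 | −0.26 | +0.30 | +0.79 |

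In the 12% row, power is 21/13/6/4%, against about 40–43% without censoring. Repeat runs moved the least stable cell of that row (baseline −12) between −0.24 and −0.32. The linear rule gives −1.48 to −1.59 throughout, with power within about 2 points of uncensored.

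Check against step 2 at baseline −8, 12% non-detects: the mean minimum is about −12.9, so the gap is 0.8 × 12.9 + 2.32 = 12.64. The bracket is 0.12 − 0.039 = 0.081, and the product is 1.02. The simulated difference is 1.01.

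*Equal effects:* the contrast stays within ±0.06 of zero and rejection is at most 5.6% in every cell. With both changes −2.0 and 12% Day 15 non-detects, the within-lesion change reads −1.33/−1.18/−0.88/−0.59. True per-gene improvement is 2.0/3 = 67%; the median reads 81/89/83/33%. It can rise because non-lesional samples are also non-detects, so the denominator shrinks too.

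**The case against.** The strongest reply is that nobody would apply the rule literally. A percentage of a minimum makes sense only for a positive quantity, and the protocol describes a ratio that is then log2-transformed. On that view this is a clarification of wording. A literal application might also be noticed: in the setting with baseline −8 and 12% non-detects, imputed values would sit near −2.6, more than 5 log2 units above the lesional mean, and SAP 6.1.2.1 tabulates quartiles and extremes.

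The possible harm is also conditional. It needs non-detects, a negative minimum and unequal changes in non-detect rate, and the documents show none of these for any key biomarker. IL-13 is only a possible case, since the protocol also puts it on the separate RT PCR panel. Sign reversal appears only at 28% non-detects with baseline −8 or −12, where about 43% of non-lesional samples are undetected too. In the runs the primary error is lost power, not false superiority.

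Most of this stands as a limit on size. It does not remove the defect. −ΔCt is the only scale the SAP defines before the rule, a programmer following the text would multiply that value by 0.2, and no other passage settles the matter. Summary tables might reveal the mistake, but they do not specify the method.

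**Conclusion.** The point holds and should be fixed before the biomarker data are analysed. As written, the rule gives a wrong ordering for any gene with a negative minimum −ΔCt. That part is exact. The size in this trial is unknown: the simulated attenuation runs from minor (−1.34 to −1.41 against −1.5 at 1% non-detects) to a reversed sign in extreme cells, and it rests on assumed abundance, non-detect rates, effects and variance components. The defect is an unspecified scale; it is not evidence that the analysis was or would be run wrongly. Genes that are always detected, genes with a positive minimum, the microarray data and TSS are unaffected.

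**What to change.** Replace the sentence in SAP 5.2.3 with: *values below the limit of detection are set to 20% of the gene's minimum on the linear scale (2^−ΔCt), that is min(−ΔCt) − log2(5), before analysis.* The same sentence can say whether the rule also covers single-gene PCR, though that is only a missing detail.

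The cost is one sentence, with no change to the analysis if the linear scale was already intended. The linear rule can slightly overstate the contrast (up to −1.59 against −1.5 at SD 3, and −1.73 at an assumed SD of 1.4). A left-censored sensitivity analysis and non-detect counts by lesion and visit are therefore reasonable extras, but optional.

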#### **7.2. Skin Biopsy Samples**

One 4.5 mm skin biopsy (punch biopsy) will be collected from each target treatment area on Day 1 and Day 15. In addition, on Day 8, subjects will be offered to have one optional 4.5 mm skin biopsy collected from each target treatment area. Subjects should not miss more than 3 IP applications in total, and have no missed IP applications the 2 days before Day 8 or Day 15 biopsy collection.

The biopsies on Day 8 and Day 15 will be collected in the vicinity, but at least 1 cm distant from where the biopsies were collected at Day 1, even if the target treatment area has cleared. One additional 4.5 mm biopsy will be collected from nonlesional skin on Day 1. Each

biopsy will be cut in half. One half will be used to perform RT PCR and gene array and the other half will be used for immunohistochemistry analysis.

Details of the biopsies sampling and handling will be described in a separate manual.

Tissue and derived material left over from the biopsy already being performed in this study may be used for potential further testing (eg, RNA-Seq analysis) provided material is available. Each sample will be labeled with a code so that the laboratory personnel (including biomarker laboratory personnel) testing the samples will not know the subject's identity. Any tissue or derived material left over may be stored long term for further research purposes at a Sponsor-designated facility. The samples will be used for the purposes described in the protocol and in the informed consent document; any other uses require additional ethical approval. Unless a time limitation is required by local regulations or ethical requirements, the samples may be stored for up to 15 years after the end of the study and then destroyed.

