5. GENERAL METHODOLOGY AND CONVENTIONS

5.1. Hypotheses and Decision Rules

One of the primary analyses will be a superiority test to demonstrate crisaborole ointment 2% is more efficacious than vehicle in the target lesion in subjects with mild to moderate AD as measured by the change from baseline in target lesion severity score (TSS) between crisaborole treated lesion and vehicle treated lesion. The null hypothesis is that there is no difference between crisaborole ointment 2% and vehicle, and the alternative hypothesis is that crisaborole ointment 2% is superior to vehicle as measured by change from baseline in TSS at Day 15. The difference between crisaborole and vehicle in TSS change from baseline at Day 15 is significant if $p\text{-value} < 0.05$.

Another primary analysis is for the change in the key skin biomarkers S100A12, CCL17, CCL18, CCL22, elafin/PI3, K16, or IL-13 in the target lesion treated with crisaborole 2% ointment or vehicle. The null hypothesis is that there is no difference between crisaborole ointment 2% and vehicle in the change from baseline to Day 15 in these biomarkers, and the alternative hypothesis is that there is a difference between crisaborole ointment 2% and vehicle in the expression level of biomarkers. Mixed effect model will be used and p-values will be adjusted by Benjamini-Hochberg procedure.

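### SAP 5.2.3 writes neither the Treatment-by-Time term nor the between-lesion Day 15 contrast that the primary biomarker hypothesis in SAP 5.1 needs, and its factor list does not fit its own within-treatment contrasts

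*SAP*

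**What the plan says.** **Hypothesis.** SAP 5.1 sets the biomarker null hypothesis as: "there is no difference between crisaborole ointment 2% and vehicle in the change from baseline to Day 15 in these biomarkers". The p-values are then adjusted by Benjamini-Hochberg.

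**PCR model.** SAP 5.2.3: "The gene expression data is modeled using a mixed effect model with Time, Tissue, and Treatment as a fixed effect", with a random intercept per patient. In praising the model's tolerance of missing data, it says that "estimation of the main effects is possible even in the presence of missing values". On contrasts it says: "Contrasts are used to estimate the fold changes with treatment within each treatment group and conduct hypothesis testing".

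**Microarray model.** The same section repeats the factor list: "Expression values are modeled using mixed-effect models with fixed factors Time, Tissue and Treatment and a random effect for each patient".

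**Decision and reporting.** SAP 6.1.2.1 refers back to 5.2.3 for the method, requires an LS mean difference with standard error, 95% CI and p-value, and concludes that "the lesion biomarker change is superior for crisaborole treated area if adjusted pvalue<0.05". SAP 6.2.2 takes the Day 8 result from the same model.

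**Samples.** Under Protocol 7.2, each target area is biopsied on Day 1 and Day 15, and optionally on Day 8. In addition, "One additional 4.5 mm biopsy will be collected from nonlesional skin on Day 1". Protocol 9.3 says only that a mixed effect model will be used.

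**The concern.** A difference between lesions in change over time is an interaction. A model that lists three factors, speaks of main effects and writes no interaction does not contain that quantity. The contrasts that are described are changes by treatment, and the per-gene improvement formula compares a lesional change with the baseline lesional versus non-lesional gap. Neither is the crisaborole versus vehicle comparison. The formula's time subscripts (W12, W0) also match no visit in this trial, so the text cannot be assumed to have been fitted to its two-lesion design.

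The TSS endpoint does not have this gap. SAP 5.2.2 makes the between-lesion difference in change the response, so the visit effect at Day 15 is the required estimate. The biomarker section has no counterpart.

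What is at stake is pre-specification of a primary analysis. Two competent analysts could follow SAP 5.2.3 and send different p-values for the same seven genes into Benjamini-Hochberg.

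**Working it through.** **1. The plan's own figures.** Protocol 9.1 gives one number for the biomarkers: a 95% half-width below 1.1 with n = 30 and SD 3. With the normal quantile, 1.960 × 3/√30 = 1.074, which agrees (the t quantile gives 1.120). This is the precision of the change within a lesion, not of the difference between lesions. The TSS powers also reproduce (difference 1.4, SD 3, one-sided 0.05 paired t-test): 89.5% at N = 40 and 80.3% at N = 30, against the stated 90% and 80%. The documents give no power or expected value for the between-lesion biomarker contrast.

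**2. The quantity SAP 5.1 tests.** Write C and V for the crisaborole and vehicle lesion and attach the day:

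Δ = (C15 − C1) − (V15 − V1).

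**3. Δ under a literal additive model of expression levels.**

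E(y) = μ + α(day) + γ·[lesional] + τ·[crisaborole].

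- C15 − C1 = (α15 + τ) − (α1 + τ) = α15 − α1
- V15 − V1 = α15 − α1
- Δ = 0 for every gene, whatever the data.

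**4. What τ would estimate.** Biopsies come in lesion pairs at each visit, so τ averages the C − V differences over all pairs. Assume equal expected Day 1 levels. Let d be the true Day 15 difference, f the share of subjects taking the Day 8 biopsy, and ρ the Day 8 difference as a fraction of d. Neither f nor ρ is in the documents, so both are varied.

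τ/d = (0 + fρ + 1)/(2 + f)

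| f | ρ = 0 | ρ = 0.5 | ρ = 1 |
|---|---|---|---|
| 0 | 0.50 | 0.50 | 0.50 |
| 0.25 | 1/2.25 = 0.44 | 0.50 | 1.25/2.25 = 0.56 |
| 0.50 | 1/2.5 = 0.40 | 0.50 | 1.5/2.5 = 0.60 |
| 1.00 | 1/3 = 0.33 | 0.50 | 2/3 = 0.67 |

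Exact generalised least squares with a random patient intercept gives the same values. At f = 0 the ratio is 0.50 at intraclass correlations of 0, 0.4 and 0.7, with or without the non-lesional sample. The Day 8 rows were run at 0.4.

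**5. On the fold scale (illustration only).** Suppose d = −1.0 log2, a 50% reduction. Then τ corresponds to a reduction of 1 − 2^(−0.50) = 29%. Over the range 0.33 to 0.67 it is 1 − 2^(−1/3) = 21% to 1 − 2^(−2/3) = 37%.

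**6. Simulation check.** 300 trials, n = 30, Day 1 and Day 15 only, d = −1.5, assumed patient SD 1.2 and residual SD 1.5.

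- Additive model: mean Treatment coefficient −0.72, a ratio of 0.48.
- With Treatment-by-Time: mean Day 15 interaction −1.51, so the full effect is recovered.
- Share of trials with unadjusted p < 0.05: 72% and 77% respectively. In this setting the main damage is to the estimate rather than to detection.

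**7. If change from baseline is the response instead.** The Day 1 pairs drop out and τ/d = (1 + fρ)/(1 + f). This is 1.00 with no Day 8 biopsies, and an average of the Day 8 and Day 15 effects otherwise (for example 0.85 at f = 1, ρ = 0.7).

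**The case against.** The strongest reply is that SAP 5.2.3 lists factors and is not a model formula. It nowhere excludes interactions. Changes by treatment can differ only if Treatment and Time are crossed. The hypothesis in 5.1, the LS mean difference in 6.1.2.1 and the separate Day 8 result in 6.2.2 all point the same way. The main-effects phrase sits in a sentence about missing values. A contrast of exactly zero for every gene would also be noticed at the first run.

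This stands, and it rules out three stronger readings that a reader might infer:

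- *That the primary biomarker result is zero by construction.* This is true only of the literal additive model, which the surrounding text contradicts.
- *That the trial will report about half the effect.* No section makes the Treatment main effect the test. SAP 6.1.2.1 also speaks of analysing change from baseline, and with that response the Day 15 effect is not halved when only Day 15 is modelled (step 7). That reading fits 5.2.3 poorly, because non-lesional skin is sampled only on Day 1 and so has no change, yet Tissue is a factor and the improvement formula needs Day 1 levels.
- *That Tissue and Treatment are fatally confounded.* Any redundancy depends on coding. With two treatment levels plus Tissue the additive matrix has full rank, and dropping a redundant column alters no estimable contrast.

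The reply does not supply what is missing. Even with crossed factors, the contrast that yields the LS mean difference and its p-value is not written anywhere.

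**Conclusion.** The point holds as a specification gap in a primary analysis: the interaction and the between-lesion contrast are unwritten, and the factor list conflicts with the contrasts and outputs that the SAP asks for. The figures are conditional. Zero applies to the SAP 5.1 contrast, and 0.50 (range 0.33 to 0.67) to the Treatment term. Both require an additive model fitted to expression levels, and the second also requires equal expected baselines. The range reflects unknown Day 8 uptake and effect. This is a should-fix clarification. The TSS analysis and its sample size are not affected.

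**What to change.** In SAP 5.2.3, for both PCR and microarray:

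1. State the fixed effects as one factor with seven levels: non-lesional Day 1; crisaborole lesion Day 1, 8 and 15; vehicle lesion Day 1, 8 and 15. Including Treatment-by-Time for the lesional samples is equivalent.
2. Name (C15 − C1) − (V15 − V1) as the primary contrast per gene. Say that it gives the LS mean difference in 6.1.2.1 and the p-value that enters Benjamini-Hochberg.
3. Keep within-lesion changes and lesional minus non-lesional as secondary contrasts.

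Forcing the two Day 1 lesional means to be equal, on the ground of randomisation, should not be added on its own. With only a random patient intercept it reduces the estimate to the raw Day 15 difference. Let r be the correlation between the Day 1 and Day 15 between-lesion differences. The variance relative to the difference in change is then 1/(2(1 − r)): 1/(2 × 0.5) = 1.0 at r = 0.5 and 1/(2 × 0.2) = 2.5 at r = 0.8. It would need a lesion-level covariance to be specified as well.

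The cost is SAP wording and a few lines of code before database release. No new data are needed, and the endpoint and the SAP 5.1 hypothesis stay as they are.

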Pruritus numerical rating scale (global)		X				X	X k	X	X	
Contraception Check g	X	X	X	X	X	X	X		X	X
Serious and non-serious adverse event monitoring	X	→	→	→	→	X	→	→	→	X

Abbreviations: → = ongoing/continuous event; AD = atopic dermatitis; BID = twice a day; % BSA = percent of body surface area; CRU = Clinical Research Unit; CCI [redacted]; ET = Early termination visit; FSH = follicle-stimulating hormone; ISGA = investigator's static global assessment; CCI [redacted]; TSS = Total Sign Score.

- Follow-up contact will be completed at least 28 calendar days after the last administration of the investigational product to capture any potential adverse events and to confirm appropriate contraception usage. Visit is planned to occur as a telephone contact.
- The Screening physical examination (full) may be performed at Baseline/Day 1 visit at the discretion of the Investigator. If full exam is completed at Screening, a limited exam should be collected at baseline. Target treatment areas must be identified at Screening and confirmed at Baseline.
- Women of childbearing potential only. Serum pregnancy test at Screening and urine pregnancy tests at all other visits.
- From Day 1 to Day 15 study treatment will be applied at the site (CRU), at regular intervals twice a day, approximately every 8 to 12 hours. From Day 15 through the end of treatment, subjects will apply open-label investigational product at home twice a day, approximately every 8-12 hours. During the open-label period, subjects will be required to complete the diary which will include dosing, adverse events and pruritus numerical rating scale information.
- On Day 15 study visit, a diary will be distributed to the subject. There will be a requirement to bring the subject diary to the subsequent visit(s) for collection and review.
- One 4.5 mm skin biopsy will be collected from each target treatment area prior to IP application on Day 1, Day 8 (optional for subjects) and Day 15. The biopsies on Day 8 and Day 15 will be collected in the vicinity, but at least 1 cm distant from where the biopsies were collected at Day 1, even if the target treatment area has cleared. One additional 4.5 mm skin biopsy will be collected from nonlesional skin on Day 1. If a subject has an early termination visit during the double-blind treatment period, every attempt should be made for the skin biopsy to be collected at this visit.

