### **5.1. Randomization**

All subjects will receive active and vehicle investigational products during the double-blind treatment period.

Each target treatment area (1 and 2) will be assigned per the randomization schedule to one of the following:

- Crisaborole ointment 2%.
- Crisaborole placebo vehicle ointment.

All subjects will receive crisaborole ointment, 2% for the open-label treatment period (following the skin biopsy on Day 15).

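### The primary biomarker test, on its natural reading, subtracts a chance Day 1 difference between two untreated, randomised lesions in full and so loses precision; SAP 5.2.3 should specify a common Day 1 lesional mean with lesion-level covariance

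*SAP*

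**What the plan says.** SAP 5.1 sets the biomarker null hypothesis as "no difference between crisaborole ointment 2% and vehicle in the change from baseline to Day 15 in these biomarkers". SAP 6.1.2.1 says that "the change from baseline in lesion biomarkers will be analyzed using the model specified in" section 5.2.3, in the per-protocol set, and concludes that "the lesion biomarker change is superior for crisaborole treated area if adjusted pvalue<0.05". The adjustment is Benjamini-Hochberg.

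SAP 5.2.3 says the expression data are "modeled using a mixed effect model with Time, Tissue, and Treatment as a fixed effect and a random intercept for each patient". On testing it adds: "Contrasts are used to estimate the fold changes with treatment within each treatment group and conduct hypothesis testing". It lists no interactions, does not say which Treatment level a Day 1 sample carries, and mentions no shared Day 1 lesional mean, baseline covariate or lesion-level covariance.

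Two design facts matter. The Protocol's Schedule of Activities states: "One 4.5 mm skin biopsy will be collected from each target treatment area prior to IP application on Day 1". Protocol 5.1 states: "Each target treatment area (1 and 2) will be assigned per the randomization schedule to one of the following", the options being crisaborole and vehicle.

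Protocol 9.1 supports n = 30 for biomarkers by the precision of the change within one lesion, a 95% half-width below 1.1. It assumes that "the maximal standard deviations for the change in FCH is 3". It gives no precision or power for the crisaborole-vehicle contrast.

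**The concern.** At Day 1 neither lesion has received product, and chance decides which lesion gets which. Expected Day 1 expression is therefore the same in the lesion about to receive crisaborole and the lesion about to receive vehicle. Any observed Day 1 difference between them is chance: sampling of small punches, assay noise and lesion-to-lesion variation.

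A raw difference in change subtracts that Day 1 difference with weight 1. This is efficient only if the lesion difference persists almost unchanged to Day 15. If it persists only partly, the subtraction adds more noise than it removes. Under a model with only a patient intercept it does not persist at all.

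This is one of the two primary analyses, run on about 30 subjects and adjusted over seven genes. Avoidable noise lowers the chance of detecting the mechanism effects that the study was set up to find.

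**Working it through.** **Inputs.** SD of one lesion's change 3 (log2) and n = 30, from Protocol 9.1. A patient random intercept only, from SAP 5.2.3. Two-sided 0.05, because the alternative in SAP 5.1 is a difference. The correlation r is not in the documents and is varied.

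**The plan's own figure.** The 95% half-width for one lesion's change is 1.96 × 3/√30 = 1.07, which reproduces the stated value below 1.1. With t on 29 df it is 1.12.

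**Variance under the SAP's model.** With a patient intercept and independent residuals of variance s², the intercept cancels within a lesion, so the change has variance 2s² = 9 and s² = 4.5.
- Raw contrast, (crisaborole Day 15 − Day 1) − (vehicle Day 15 − Day 1): 4s²/n = 18/30 = 0.60, SE 0.775.
- One shared Day 1 lesional mean: 2s²/n = 9/30 = 0.30, SE 0.548.

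The ratio is 2.00. It is the same for patient-intercept variances of 0.5, 4.5 and 20, with or without Day 8. In 300 simulated mixed-model fits the mean model-based variances were 0.599 and 0.300; the empirical ratio was 1.85, consistent with 2 for that number of runs.

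**General case.** Let D1 and D15 be the within-patient lesion differences, each with variance v, and with correlation r.
- Raw difference in change: 2v(1 − r).
- Efficient use of D1: v(1 − r²).
- Ratio: 2(1 − r)/(1 − r²) = 2/(1 + r).

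Holding the SD of change at 3 makes the raw contrast variance 18/n and the efficient one 9(1 + r)/n:

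| r | 2/(1+r) | Ratio with weight estimated, n = 30 (simulated) | Half-width, raw | Half-width, efficient | Power, if raw has 80% |
|---|---|---|---|---|---|
| 0 | 2.00 | 1.95 | 1.52 | 1.07 | 98% |
| 0.3 | 1.54 | 1.49 | 1.52 | 1.22 | 93% |
| 0.5 | 1.33 | 1.28 | 1.52 | 1.31 | 90% |
| 0.7 | 1.18 | 1.14 | 1.52 | 1.40 | 86% |

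Half-widths use z. Power takes the weight as known and is before Benjamini-Hochberg adjustment. A normal check at r = 0.5: 80% power means effect/SE = 2.80; 2.80 × √1.333 = 3.23; 3.23 − 1.96 = 1.27, which gives 90%. At r = 0.9 the simulated ratio is 1.01, so almost no gain remains.

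**Detectable difference at r = 0** (80% power, t on 29 df): 2.25 log2 units raw and 1.59 with the shared mean. With z these are 2.17 and 1.53.

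**A trap in the remedy.** A shared Day 1 mean with only a patient intercept gives D1 no weight, so the variance is v and the ratio of raw to constrained is 2(1 − r). That is 1.0 at r = 0.5 and 0.6 at r = 0.7. Beyond r = 0.5 the constraint alone is worse than the raw difference in change.

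**The case against.** **The model is not fully written out.** SAP 5.2.3 names three factors and no interactions. If untreated Day 1 samples share one Treatment level, the common mean is already in place. A main-effects-only model could not test the null in SAP 5.1 at all. The alternative in SAP 5.1 speaks of expression level rather than change. The improvement formula in 5.2.3 has a single lesional baseline term with no treatment index, but its follow-up term has none either, so it settles nothing. This objection stands: a reader might infer that the SAP prescribes separate Day 1 means, and it does not say so. Separate means are only the natural reading of 5.1, 5.2.3 and 6.1.2.1 together.

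**Doubling is an extreme.** Later biopsies come from the same mapped area, near the Day 1 site, so some persistence of lesion differences is plausible. This also stands. For r of 0 or more, 2.0 is the upper limit, and the range has to be reported.

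**Change from baseline is the prespecified endpoint, and the sample size rests on precision, not power.** Both are true, and they keep this a matter of efficiency. They do not rule out the change. With equal expected Day 1 means, the difference in Day 15 means and the difference in changes are the same quantity, so the endpoint is kept and estimated more precisely.

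**The microarray model is a separate matter.** Agreed. It uses moderated paired tests over many probe-sets and is not the seven-gene primary analysis.

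**Conclusion.** The point holds as a precision loss in the primary analysis of the seven key biomarkers. The design guarantees equal expected Day 1 levels, and the SAP states nothing that uses this. The variance is inflated by 2/(1 + r): 2.0 under the SAP's patient-only intercept, 1.54 at r = 0.3, 1.33 at 0.5 and 1.18 at 0.7, and slightly less once the weight is estimated from 30 subjects.

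The ratio does not depend on the SD. The half-widths and detectable differences do, and they are upper values because SD 3 is a stated maximum. The result assumes that per-protocol exclusions, made by subject, do not disturb the balance of Day 1 levels between the two lesions.

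A reader might go further and infer that the planned test is biased or invalid, or that the variance is certainly doubled. The documents support neither. If its covariance is right, the planned contrast is valid, and r is unknown. This is an improvement worth making, not an error that must be corrected.

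**What to change.** In SAP 5.2.3, for the PCR model of the seven key biomarkers:

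- Write out the cell means: non-lesional Day 1, one common lesional Day 1 mean for both target lesions, then separate crisaborole and vehicle means at Day 8 and Day 15.
- Add a lesion-within-patient random effect or an unstructured lesion covariance, so that the data set the weight given to Day 1. Do not add the constraint to a patient-only intercept.
- Name the Day 15 crisaborole-vehicle contrast from this model as the primary test, and state the equal-Day-1-mean assumption with randomisation of lesions as its reason.
- Keep the raw changes by treatment as descriptive output.

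For complete pairs, an equivalent form regresses the Day 15 lesion difference on the uncentred Day 1 lesion difference and tests the intercept.

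The cost is SAP wording and a revised model specification; no new data are needed. The estimate will no longer equal the difference of the tabulated mean changes, which a table footnote can explain. The sponsor should also judge whether this counts as a major modification of a primary analysis, which Protocol section 9 says must appear in an amendment; Protocol 9.3 itself specifies only a mixed effect model. The microarray model need not change.
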